8.3. Other Safety Analyses

The analyses of non-laboratory safety test results including vital signs will be based on GSK Core Data Standards, unless otherwise specified.

8.3.1. Vital Signs

Summary statistics of observed vital signs will be presented by visit [T3.41]. Summary statistics of change from baseline in vital signs will also be presented by visit [T3.42].

A listing of vital signs will be presented by subject [L3.10].

8.3.2. Device Malfunction

A listing of device malfunction will be provided by subject and date of malfunction [L1.10].

8.3.3. Possible Suicidality-Related Adverse Event

A listing of possible suicidality-related adverse event data will be presented [L3.11].

9. PHARMACOKINETIC ANALYSES

9.1. Primary Pharmacokinetic Analyses

The PK analyses will be based on the PK population. See 'RAP mock outputs 200908' document for mock displays.

PK outputs will report all On Study data (see Section 5.2). On-treatment PK data will be summarised using a treatment policy approach, including all data regardless of any Intercurrent Events (ICE). Week 8 Follow Up data will only be summarised if the subject has stopped their study treatment and hasn't taken any concomitant Belimumab during the follow-up period.

Descriptive statistics for observed belimumab concentrations will be displayed for each scheduled visit where pre-dosing PK samples are available for analysis. Each of the three cohorts will be summarized separately and overall [T5.01], and the following statistics will be displayed: number of subjects, mean value, standard deviation, 95% confidence interval, geometric mean, geometric standard deviation, geometric 95% confidence interval, geometric coefficient of variation (%), median, 25th and 75th percentiles, minimum, and maximum. No statistical tests will be performed.

The geometric mean, standard deviation and confidence interval are calculated at each visit using all of the non-zero PK concentration values. These non-zero concentration values are log transformed and the arithmetic mean, standard deviation and confidence interval are calculated. The geometric mean, geometric standard deviation and geometric confidence intervals are the exponentials of these values.

The geometric Coefficient of Variation is calculated as follows:

$$CV(\%) = \sqrt{exponential(logSD^2) - 1} * 100$$

where logSD is the standard deviation of the log-transformed concentrations.

A graph will be produced which displays the median pre-injection belimumab concentrations (+/- interquartile range) by visit through Week 52 for all subjects [F5.01], as well as by cohort [F5.02].

Additionally, a line graph will be produced which displays the geometric mean preinjection belimumab concentrations (with 95% Confidence Interval) by visit through Week 52 for all subjects [F5.03], as well as by cohort [F5.04].

A listing of belimumab PK concentration-time data will be presented by subject [L5.01].

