1. If participants withdraw from treatment prior to Week 52, in addition to the 8- and 16-week follow-up visit and assessments, an early withdrawal (EW) visit should, if possible, be completed. The EW visit requires identical assessments and procedures to the Week 52 visit. The 8- and 16-week follow-up visits are **NOT** required for participants who are eligible for and are enrolled into the optional access extension phase.
2. 16-week follow-up requires a phone call to collect AEs, concomitant medications and report results of home urine pregnancy test (if applicable) for female participants. NOTE – the 16-week follow-up may be performed at a clinic visit per local requirement.
3. An abbreviated/symptom-driven exam can be done as described in Section 8.8.1
4. Please refer to Section 8.9.1 for the time period for collection of AEs/SAEs.
5. Urine pregnancy test is sufficient for all visits in Part B. A home pregnancy test (urine) will be provided to participants for the 16-week follow-up pregnancy assessment.
6. Cohort 1 (\geq 50 kg at baseline): Study drug to be administered weekly. Wherever the dosing days coincide with clinic visits IP administration in clinic is mandated. PK and/or biomarker sample collection, where specified, must be pre-dose at these visits.
7. Cohort 2 (\geq 30 kg - <50 kg at baseline): Study drug to be administered every 10 days. Wherever the dosing days coincide with clinic visits IP administration in clinic is mandated. PK and/or biomarker sample collection, where specified, must be pre-dose at these visits.
8. Cohort 3 (15 - <30 kg at baseline): Study drug to be administered every 2 weeks. Wherever the dosing days coincide with clinic visits IP administration in clinic is mandated. PK and/or sample collection, where specified, must be pre-dose at these visits.

9. In Part B the dosing frequency may be switched according to any change in body weight. Please refer to Section [6.6](#) Dose Modification. IF a participant switches dosing frequency due to weight changes during Part B, the last IP administration will be according to the schedule provided at Week44. Individual cases will be consulted with and resolved by the Medical Monitor.
10. Samples must be taken pre-dose where the dose is administered on a clinic visit day.

1.3.4. SOA 4 Optional Access Extension Phase - Applies exclusively to eligible participants who complete Part B

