- Is not a woman of childbearing potential (WOCBP) (See [Appendix 4](#))

OR
- Is a WOCBP and is using a contraceptive method that is highly effective, with a failure rate of <1%, as described in [Appendix 4](#) during the belimumab treatment period and for at least 16 weeks, corresponding to the time needed to eliminate any study intervention(s) (e.g., 5 terminal half-lives), after the last dose of study intervention. The investigator should evaluate the effectiveness of the contraceptive method in relationship to the first dose of study intervention.
- A WOCBP must have a negative highly sensitive [[Appendix 2](#)] pregnancy test (serum or as required by local regulations) within 35 days before the first dose of belimumab.
- The investigator is responsible for review of medical history, menstrual history, and recent sexual activity to decrease the risk for inclusion of a woman with an early undetected pregnancy.

Informed Consent

8. Participant signs and dates a written age appropriate assent form (in accordance with applicable regulations) and the parent or legal guardian (or emancipated minor) that has the ability to understand the requirements of the study, provides written informed consent (including consent for the use and disclosure of research-related health information) that the participant will comply with the study protocol procedures (including required study visits).

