6.6. Dose Modification

No dose modifications of belimumab are allowed. An exception is for a participant whose body weight changes within pre-defined criteria.

The participant must be weighed prior to dosing at each clinic visit and dosing frequency for the next period adjusted according to the criteria below. Site personnel should ensure they provide the participant with sufficient autoinjectors for possible home use prior to the next clinic visit. (See additional details in the SRM).

Part A		Part B and Optional Access Extension Phase		
Dosing cohort	Dosing frequency	Body weight (BW)	Dosing frequency	Note
Cohort 1 (BW ≥ 50 kg at baseline)	Every week	Remains ≥ 50 kg	Every week	
		Decreases to <50 kg	Every 10 days	Revert to every week if BW increases to ≥ 53 kg
Cohort 2 (BW ≥ 30 kg and <50 kg at baseline)	Every 10 days	Remains ≥ 30 kg and <50 kg	Every 10 days	
		Increases to ≥ 53 kg	Every week	Revert to every 10 days if BW decreases to <50 kg
		Decreases to <30 kg	Every 2 weeks	Revert to every 10 days if BW increases to ≥ 33 kg
Cohort 3 ^a (BW <30 kg at baseline)	Every 2 weeks	Remains <30 kg	Every 2 weeks	
		Increases to ≥ 33 kg	Every 10 days	Revert to every 2 weeks if BW decrease to <30 kg

a. If BW drops below 15 kg at any time, suspend dosing and discuss with Medical Monitor to determine if participant should be withdrawn from the study.

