At baseline, each subject is allocated to a treatment cohort according to their body weight, which dictates the dosing schedule for the subject (Protocol Section 4.1). During Part A, subjects should remain in the same dosing group. During Part B, the dosing group may remain the same or may require a change, according to the subjects' body weight (Protocol Section 6.6). A shift table that summarizes the differences between dosing group at baseline compared to the last observed dosing group (based on the last treatment date) will be provided [T1.12]. Subjects who withdraw from the study during Part A will be assumed to have remained in their original dosing group.

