7.1.3. Subgroup, Supportive and Sensitivity Analyses

Summaries will be presented by baseline weight cohort and overall. There are no planned supportive or sensitivity analyses for the exploratory efficacy endpoints. Posthoc analyses may be considered for other subgroups.

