13.4.2. Study Population

Age Derivation

If the day of date of birth is unavailable, age on any specified day (e.g. screening, 1st dose etc.) will be derived as:

If the specified day is on or after the 15th of the birth month then:

Year of specific timepoint – DOB year

If the specified day is before the 15th of the birth month then:

(Year of specific timepoint – DOB year) - 1

Age at screening will be defined as the screening date, and derived as above.

Age Derivation

Extent of Exposure

- Number of days of exposure to study drug will be calculated based on the formula:

 Duration of Exposure in Days = Treatment Stop Date (Treatment Start Date) + X,
 where X is 7, 10, or 14 for the three weight cohorts respectively.
- Only complete dates will be used when calculating duration of exposure. First and last injection dates will be used, regardless of any missing doses.
- Participants who were enrolled but did not report a treatment start date will be categorised as having zero days of exposure.

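### After Week 12 the SAP still groups belimumab concentrations by baseline weight cohort although dosing frequency can change in Part B, so the Week 16 to 52 cohort entries can mix regimens; the exposure-duration formula has the same gap.

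*SAP*

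**What the plan says.** The SAP uses two terms. The cohort is fixed at entry: "At baseline, each subject is allocated to a treatment cohort according to their body weight" (SAP 6.1). The dosing group can move: "During Part B, the dosing group may remain the same or may require a change, according to the subjects' body weight" (same section). The protocol agrees. Section 6.6 has the child weighed at each clinic visit and the "dosing frequency for the next period adjusted according to the criteria below", and the Part B schedule repeats that "In Part B the dosing frequency may be switched according to any change in body weight".

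Under Protocol 6.6, Cohort 1 can move from weekly to 10-day dosing, Cohort 2 from 10-day to weekly or 2-weekly dosing, and Cohort 3 from 2-weekly to 10-day dosing, with reversion possible. Dosing group is meant to stay fixed in Part A.

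SAP 9.1 tabulates pre-dose concentrations at each scheduled visit: "Each of the three cohorts will be summarized separately and overall" (T5.01). It plots medians (F5.02) and geometric means (F5.04) by cohort through Week 52. A treatment policy approach keeps all on-treatment data. Part B PK samples fall at Weeks 16, 24, 36 and 52, plus the 8-week follow-up.

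Switching itself is displayed only in T1.12, which sets the baseline dosing group against the last one. L1.11 lists the dosing cohort for each injection. Duration of exposure (SAP 13.4.2) is last minus first treatment date plus X, "where X is 7, 10, or 14 for the three weight cohorts respectively".

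**The concern.** In Part A, cohort and regimen are the same thing, and the protocol names each cohort by its dosing frequency. A reader will carry that pairing into Part B and take the Cohort 2 curve as the 10-day profile. After Week 12 that is no longer assured. A child who has switched contributes concentrations from another regimen, plus carry-over from the old one, under the old label. With about 28 children in three cohorts, a few switchers could look like drift in exposure over time.

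No planned output resolves this. T1.12 does not show when a switch happened, misses a child who switches and reverts, and is not linked to the PK displays. The exposure formula has the same weakness on a smaller scale.

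**Working it through.** **1. Which grouping SAP 9.1 means.** It writes only cohort. SAP 6.1 ties that word to baseline weight, and for efficacy SAP 7.1.3 is explicit: "Summaries will be presented by baseline weight cohort and overall". The baseline reading is the natural one. If the regimen in force was intended, the text does not say so.

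**2. Reproducing the protocol's exposure figures (Protocol 4.3, Table 1).** With linear PK, Cavg at fixed weight and dose is proportional to 1/interval.
- 30 kg, 2-weekly to 10-day: 88 × 14/10 = 123.2 (stated 123 µg/mL).
- 50 kg, 10-day to weekly: 90 × 10/7 = 128.6 (stated 129 µg/mL).

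**3. One-step switch at fixed weight.**
- Upward: 123/88 = 1.40 and 129/90 = 1.43, so +40% and +43%.
- Downward: 88/123 = 0.72 and 90/129 = 0.70, so −28% and −30%.
- Pre-dose troughs, which are what T5.01 reports, differ more. Steady-state superposition in a one-compartment model (assumed half-life 14 to 22.4 days; bolus input or absorption rate 0.2 to 0.4 per day) gives adjacent-regimen ratios of 1.46 to 1.56, and weekly to 2-weekly ratios of 2.1 to 2.4.

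**4. Displacement from the cohort centre.** Protocol 4.3 centres all three groups on 104 µg/mL, so this is the comparison that matters for a cohort curve. Upward switches happen at 33 or 53 kg, not at the threshold. I interpolate log Cavg on log weight in Table 1.
- 10-day regimen, 30 kg (123) to 50 kg (90): slope ln(90/123)/ln(50/30) = −0.61. At 33 kg, 123 × (33/30)^−0.61 = 116, and 116/104 = +12%.
- Weekly regimen, 50 kg (129) to the adult entry at 67 kg (104): slope ln(104/129)/ln(67/50) = −0.74. At 53 kg, 129 × (53/50)^−0.74 = 124, and 124/104 = +19%.
- Downward, at the threshold: 90/104 = −13% and 88/104 = −15%.
- Effect on mean Cavg: one in 3 at +12% gives 12/3 = 4%; two in 10 at +19% gives 2 × 19/10 = 3.8%.

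**5. Who can switch in time to affect a sample.** The documents give no count. The girls' median weights quoted in Protocol 4.3 imply (50.0 − 30.1)/(14.2 − 9.3) = 4.06 kg/year.
- An upward switch needs 3 kg beyond the threshold. Even from the very top of a cohort that takes 3/4.06 = 0.74 year, about 38 weeks, which is after the Week 36 sample.
- Frequency changes at a clinic visit for the following period, so Week 44 is the only visit at which such a switch can still affect the Week 52 sample.
- Growth by Week 44 is about 3.42 kg, or 0.42 kg past the buffer. With baseline weights assumed uniform, that is 0.42/20 = 2.1% of Cohort 2 and 0.42/15 = 2.8% of Cohort 3.
- Downward switches have no buffer. Falling just below 50 or 30 kg is enough, from the start of Part B. The documents give no basis for a rate.

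**6. Carry-over.** Protocol 5.1 sets at least 16 weeks of contraception, "corresponding to the time needed to eliminate any study intervention(s) (e.g., 5 terminal half-lives), after the last dose". That supports 112/5 = 22.4 days as an upper bound on half-life; the lower end of 14 days is my assumption. The share of the old-to-new difference remaining after t days is 2^(−t/half-life):

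| Days since switch | 14-day half-life | 22.4-day half-life |
|---|---|---|
| 28 | 25% | 42% |
| 56 | 6% | 18% |
| 84 | 2% | 7% |

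**7. Exposure formula.** For a one-step switcher X is wrong by 10 − 7 = 3 days or 14 − 10 = 4 days, about 1% of 364 days.

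**The case against.** The strongest reply is that SAP 9.1 labels these displays by cohort, not by regimen, and declares a treatment policy approach. Exposure by starting group under a weight-adjusted dosing rule is a coherent quantity. That stands, and it is why the baseline-cohort displays should stay. It does not tell the reader which Part B samples come from another regimen.

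The reply also limits the size, and that stands too. Protocol 4.3 describes between-subject variability not explained by weight as much larger than the threshold deviations, and F5.02 uses medians and interquartile ranges, which a single switcher moves little. The listings L1.11 and L5.01 would let a determined reader reconstruct the regimens.

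Several stronger readings are tempting but not supported:
- A reader might infer that the primary endpoint is compromised. Week 12 precedes any weight-based switch. The inference on weight dependence comes from the population PK model (SAP 10.1), whose detailed plan is separate, not from these displays.
- A reader might take 40-43% as the distortion and compute 0.40/3 = 13% for one switcher in 3, or 2 × 0.43/10 = 9% for two in 10. That compares a child with the same child unswitched, not with the cohort centre.
- A reader might project growth to Week 52: (4.06 − 3)/20 = 5% of Cohort 2 and (4.06 − 3)/15 = 7% of Cohort 3. A crossing first seen at Week 52 cannot affect that visit's sample.
- A reader might treat 22 days as the half-life. The contraception wording only bounds it.

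Replacing the cohort displays, or dropping every sample within 12 weeks of a switch from the main statistics, would also go too far. It would discard the Week 52 sample of every Week 44 switcher, and groups redefined by post-baseline weight can show apparent drift of their own.

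**Conclusion.** The gap is real and confined to Part B. From Week 16 to Week 52 the by-cohort rows of T5.01 and the curves in F5.02 and F5.04 can mix regimens, and the SAP provides no flag, count or alternative grouping at visit level.

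The expected effect on mean Cavg is modest: roughly 4% for one upward switcher in 3 or two in 10. Troughs are affected more, and recent switchers are still in transition. On the implied growth rate, upward switching touches only the Week 52 on-treatment sample, in about 2-3% of Cohorts 2 and 3. Downward switching is the open quantity. These sizes assume linear PK, groups centred on 104 µg/mL, median growth, uniform baseline weights and a half-life of 14 to 22 days.

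The X term in the exposure formula is wrong by 3 to 4 days for a one-step switcher: small, but simple to correct. This should be fixed in the SAP; it does not threaten the primary result.

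**What to change.** Keep the baseline-cohort displays as the declared treatment policy summary. For visits after Week 12:
- Derive for each PK sample the dosing frequency in force at the last dose before it, from the injection data behind L1.11, and flag samples taken after a switch.
- Report the number of switchers by visit and cohort alongside T5.01, F5.02 and F5.04.
- Add one summary of concentrations by the frequency in force, with a version that omits post-switch samples.

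In SAP 13.4.2, define X as the interval of the regimen in force at the last dose.

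The cost is one derived variable, one added display and a few lines of SAP text. The by-frequency groups will be small and vary by visit. No treatment, sampling or endpoint changes.

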10. POPULATION PHARMACOKINETIC (POPPK) ANALYSES

The primary goal of this analysis is to characterize the population pharmacokinetics of belimumab administered subcutaneously in pediatric participants with systemic lupus erythematosus.

A brief summary of the planned analysis is presented below. A complete analysis plan for the popPK analyses will be reported separately.

10.1. Statistical Analyses / Methods

All analyses will be carried out on the Modelling and Analysis Platform (MAP), a validated and version-controlled system. To support the analysis a PopPK dataset will be generated from the source data. Details of the dataset specification will be provided in the separate popPK reporting and analysis plan. All pharmacokinetic data will be stored in the Archives, GlaxoSmithKline Pharmaceuticals, R&D.

Belimumab SC concentration-time data will be subjected to nonlinear mixed effects modelling using the program NONMEM to develop a population PK model for SC dosing to pediatric patients with SLE.

The influence of subject level baseline characteristics on the pharmacokinetics of belimumab SC in this patient population will be investigated, including the allometric effects of body size.

Individual estimated PK parameters (clearance, volume of distribution at steady state and terminal phase half-life) and belimumab exposure parameters at steady state (minimum, average and maximum concentration and the area under the curve over a 7-day dosing period) will be summarized descriptively and compared with the corresponding PK parameters from the pediatric IV study [BEL114055].

The population PK model will be used to assess the dependence of belimumab exposure on body weight to inform SC dose selection in low body weight pediatrics, who may require less-frequent administration compared to the weekly SC dosing frequency approved for adults.

11. PHARMACODYNAMIC AND BIOMARKER ANALYSES

Autoantibodies, Serum Immunoglobulin Isotypes, Serum Complement, Peripheral Lymphocytes including B lymphocytes and Proteins will be collected according to the Schedule of Activities (Protocol Section 1.3).

All biomarker analyses will be performed on the ITT Population. See 'RAP mock outputs 200908' document for mock displays.

Biomarker outputs will report all On Study data (see Section 5.2). Biomarker data will be summarised using a treatment policy approach, including all data regardless of any Intercurrent Events (ICE).

The specific biomarkers analysed are listed in Table 6.

Table 6 Biomarkers for Analysis

		Parameter Code (LBTESTCD)
Serum Immunoglobulin	Immunoglobulin A (g/L)	IGA
Isotypes	Immunoglobulin G (g/L)	IGG
	Immunoglobulin M (g/L)	IGM
	Anti-dsDNA Antibody (IU/mL)	ADSDNAAB

Autoantibodies and C	Antinuclear Antibodies (titer)	ANA
Reactive Protein	C Reactive Protein (mg/L)	CRP
Serum Complement	Complement C3 (mg/dL)	C3
·	Complement C4 (mg/dL)	C4
Peripheral Lymphocytes (B cells)	CD19+ Total B cells (cells/mL)	CD19
	B cells CD20+ (cells/mL)	CDX111
	Memory B cells CD20+ CD27+ (cells/mL)	CDX732
	Naive B cells CD20+ CD27- (cells/mL)	CDX731
	Plasmablasts CD27b CD38b (cells/mL)	CDX734

Note that, Plasmablasts CD27b CD38b was previously referred to as SLE subset plasmablasts.

Note that BLyS (free) Protein is only collected at Baseline and will be summarized in the study population outputs.

A listing of all biomarker results including both autoantibodies (ANA, Anti-dsDNA, CRP, BLyS (free) protein) and serum complement (C3, C4) will be presented [L4.01]. Additionally, a listing of B cell results will be presented [L4.02].

11.1. Secondary Endpoint - Pharmacodynamic and Biomarker Analyses

11.1.1. Endpoint / Variables

The change from baseline and percentage change from baseline will be evaluated by visit for each of the biomarkers listed in Table 6.

11.1.2. Population of Interest

The biomarker analyses will be based on the ITT population.

11.1.3. Strategy for Intercurrent (Post-Randomization) Events

The analyses will be performed on the observed data. No imputation will be carried out for missing data.

11.1.4. Change from Baseline

Change from baseline will be summarized by visit for the following:

- Immunoglobulin levels for all subjects [T4.02]
- B-cells for all subjects [T4.11]
- Autoantibody levels among subjects who were positive at baseline (ANA Index ≥80 titer; anti-dsDNA ≥ 30 IU/mL; CRP ≥ 4 mg/L) [T4.05]. Note that positive baseline assessments are assessed at a parameter level, e.g. the anti-dsDNA summary will include all subjects who were positive at baseline for anti-dsDNA.
- Complement levels among subjects with low values at baseline (C3<90 mg/dL; C4 < 13 mg/dL) [T4.08]. Note that low baseline assessments are assessed at a

parameter level, e.g. the C3 summary will include all subjects who were low at baseline for C3.

No statistical tests will be performed.

A figure of median change from baseline (+/- Interquartile Range) will be produced by visit for complement levels for subjects with low complement at baseline [F4.04].

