3. OBJECTIVES AND ENDPOINTS

Objective	Endpoint
Primary - Pharmacokinetics	

 To characterize the PK profile of belimumab 200 mg SC in pediatric SLE participants. 	
 Observed belimumab concentrations at Week 12. Steady-state PK parameters: Cavg (AUC), Cmax, Cmin (based on population PK estimates).
Secondary - Safety	

 To evaluate the safety and tolerability of belimumab 200 mg SC in pediatric SLE participants. 	
 Incidence of adverse events, serious adverse events and adverse events of special interest through Week 52.
Secondary - Biomarkers	

 To characterize the pharmacodynamic profile of belimumab 200 mg SC in pediatric SLE participants. 	
 Change from baseline in biomarkers (C3/C4, anti-dsDNA, B cell subsets, and immunoglobulins) at Weeks 12 and 52.
Other - Efficacy	

 To characterize the impact of belimumab 200 mg SC on disease activity in pediatric SLE participants. 	
 Percent of subjects with a ≥ 4 point reduction from baseline in SELENA SLEDAI at Weeks 12 and 52.

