9.3.3. Pharmacodynamic Analyses

All pharmacodynamic analyses will be performed on the ITT Population.

Endpoint	Statistical Analysis Methods
Secondary	
Endpoints:
 
Change from baseline in biomarkers (C3/C4, anti-dsDNA, B cell subsets, and immunoglobulins) at Weeks 12 and 52.
 
Analysis:
 
Descriptive statistics will be used to summarize change from baseline in biomarkers (C3/C4, anti-dsDNA, B cell subsets, and immunoglobulins) at Weeks 12 and 52.

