2.1. Changes to the Protocol Defined Statistical Analysis Plan

There were no changes to the originally planned statistical analysis specified in Protocol amendment 4.

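### The SAP summarises numeric change in C3/C4 only in participants low at baseline, and in anti-dsDNA only in those positive at baseline, so the protocol's ITT secondary endpoint is not produced for these markers

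*SAP*

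**What the plan says.** **Protocol.** Section 3 lists as a secondary endpoint: "Change from baseline in biomarkers (C3/C4, anti-dsDNA, B cell subsets, and immunoglobulins) at Weeks 12 and 52". Section 9.3.3 adds: "All pharmacodynamic analyses will be performed on the ITT Population". The ITT definition under Section 9.2 requires only treatment assignment and one dose. It sets no condition on baseline markers.

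**SAP, general statements.** SAP 2.2 repeats the endpoint. SAP 11.1.1 says: "The change from baseline and percentage change from baseline will be evaluated by visit for each of the biomarkers listed in Table 6". Table 6 includes C3, C4 and anti-dsDNA. SAP 11.1.2 says: "The biomarker analyses will be based on the ITT population".

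**SAP, actual displays (11.1.4 and 11.1.5).** The first item in the change list is "Immunoglobulin levels for all subjects [T4.02"], and B cells are treated the same way (T4.11). The other two items are narrower: "Autoantibody levels among subjects who were positive at baseline" (anti-dsDNA at or above 30 IU/mL) and "Complement levels among subjects with low values at baseline" (C3 below 90 mg/dL, C4 below 13 mg/dL). Both cut-offs apply marker by marker, and the percentage-change list carries the same limits.

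**SAP 2.1.** "There were no changes to the originally planned statistical analysis specified in Protocol amendment 4".

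**The concern.** Two things look wrong.

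First, for C3, C4 and anti-dsDNA the display specification does not deliver the endpoint that the protocol and the SAP's own general statements describe. The restriction is not loose wording, because the same lists explicitly cover everyone for the other markers. It appears under the secondary-endpoint heading, is not labelled as a subgroup, and is not declared as a change.

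Second, the restriction has a direction. Under SAP 5.4 baseline is the latest non-missing pre-dose value. That one value decides who enters the table and is also subtracted to form the change. Participants picked because a noisy value was low will tend to be higher next time, and those picked because it was high will tend to be lower. In a single-arm trial nothing separates that drift from a drug effect, and for complement and anti-dsDNA the drift is in the favourable direction.

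At stake is how the PD profile is read. No hypothesis test or decision rule depends on these tables.

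**Working it through.** **Step 1. Which displays could hold the missing summary?**

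| Display | Content | Numeric change for all ITT? |
|---|---|---|
| T4.07, T4.08, F4.03, F4.04 | C3/C4 change or percentage change | No, low at baseline only |
| T4.04, T4.05, F4.02 | Anti-dsDNA change or percentage change | No, positive at baseline only |
| T4.06, T4.09 (SAP 11.2, 11.2.4) | Shifts for both baseline categories | No, categories only |
| L4.01 (SAP 11) | Individual results | No, a listing |
| T1.15, T1.16 (SAP 6.2) | Baseline levels | No, baseline only |
| T3.18–T3.21 (SAP 8.2, Table 5) | Laboratory values by visit | No, complement and anti-dsDNA not included |

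None fills the gap. The mock shells were not available to check.

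**Step 2. Can the omitted participants exist?** Yes. Inclusion criterion 4 (Protocol 5.1) accepts a positive ANA alone, so anti-dsDNA negatives can enter. Low complement is not an entry requirement. SAP 11.2.4 itself provides for negative and for normal/high participants.

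**Step 3. How large could the drift be with no drug effect?** The plan states no figure to reproduce. It gives neither the share abnormal nor the correlation, so both are assumed.

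- Planned size: 24 evaluable at Week 12 (Protocol 9.2).
- Share abnormal at baseline, *p*: assumed 0.3, 0.5, 0.7.
- Correlation between baseline and later value, *ρ*: assumed 0.5, 0.7, 0.9.
- Model: bivariate normal, equal means and SDs at both times. Abnormal means the lowest fraction *p*; anti-dsDNA is the mirror image.

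With *z* the *p*-quantile of the standard normal and λ = φ(*z*)/*p*:

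- Expected subset change = (1 − ρ)λ, in SD units.
- Variance of one participant's change within the subset = (1 − ρ)²(1 − *z*λ − λ²) + 1 − ρ².
- Chance that the subset mean moves toward normal ≈ Φ(√n × mean / SD), with n = 24*p* rounded.
- Expected shifts in each direction = 24 × [*p* − P(abnormal at both times)].

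Worked case, *p* = 0.3 and ρ = 0.5: *z* = −0.524, φ(*z*) = 0.3477, λ = 0.3477/0.3 = 1.159. Expected change = 0.5 × 1.159 = 0.58 SD. Variance = 0.25 × 0.265 + 0.75 = 0.816, so SD = 0.903. With n = 7 the chance is Φ(2.646 × 0.579/0.903) = 0.96. P(abnormal at both times) = 0.157, so shifts each way = 24 × (0.300 − 0.157) = 3.4.

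| *p* (n of 24) | ρ | Expected change, SD | Chance subset mean moves toward normal | Shifts each way, of 24 |
|---|---|---|---|---|
| 0.3 (7) | 0.5 | 0.58 | 0.96 | 3.4 |
| | 0.7 | 0.35 | 0.90 | 2.6 |
| | 0.9 | 0.12 | 0.76 | 1.5 |
| 0.5 (12) | 0.5 | 0.40 | 0.93 | 4.0 |
| | 0.7 | 0.24 | 0.87 | 3.0 |
| | 0.9 | 0.08 | 0.74 | 1.7 |
| 0.7 (17) | 0.5 | 0.25 | 0.86 | 3.4 |
| | 0.7 | 0.15 | 0.80 | 2.6 |
| | 0.9 | 0.05 | 0.68 | 1.5 |

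In the same model the all-participant mean change has expectation 0, and the expected shifts toward and away from normal are equal. T4.06 and T4.09 are therefore a partial check, provided both directions are read.

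**Step 4. How many participants are left out?** Of about 28 enrolled, shares of 0.3, 0.5 and 0.7 put about 8, 14 and 20 in the numeric tables and leave out about 20, 14 and 8.

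**The case against.** The strongest reply is that little is lost. Numeric change is still summarised at every visit for the participants in whom it matters most clinically. Everyone with data enters the two-way shift tables, and individual values are listed. A subset of ITT might even be read as based on ITT. For anti-dsDNA the restriction looks like a deliberate convention, because T1.15 also summarises it continuously only in positives. Everything is descriptive.

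Part of this stands. The abnormal-at-baseline summaries are sensible and should stay, and the missing summary could be rebuilt from collected data. But the protocol endpoint is numeric change without a baseline condition. A shift table hides movement within a category, and a listing is not a summary. The convention argument does not extend to complement, which T1.16 summarises continuously for everyone.

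The illustration also has fair limits:

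- One symmetric normal model may suit anti-dsDNA poorly if many negatives sit at a reporting floor.
- The model describes a mean in SD units. The three restricted figures show medians with interquartile ranges, and two of them (F4.02, F4.03) show percentage change.
- Zero expected drift for all participants ignores entry selection. Screening requires autoantibody positivity and a SELENA SLEDAI score of at least 6, and that score counts low complement and raised DNA binding (Protocol 5.1, 10.10). Some drift may remain in the all-ITT summaries.

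These points soften the size of the contrast. They do not touch the mismatch between the stated endpoint and the specified displays.

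**Conclusion.** The concern holds. For C3, C4 and anti-dsDNA the secondary endpoint is produced only for a baseline-selected part of the ITT population, and the departure is undeclared. That conclusion rests on the text alone; the one caveat is that the mock shells were not seen. If they do contain all-ITT tables, the SAP text still needs to say so.

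The directional drift of 0.05–0.58 SD, with a 68–96% chance that the subset mean moves toward normal under no effect, rests on the assumed shares, correlations and normal model. It should be read as an indication of size only. Because the analysis is secondary and descriptive, this should be corrected, but it does not threaten the primary PK objective.

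**What to change.** Add to SAP 11.1.4, in wording such as:

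> Change from baseline in C3, C4 and anti-dsDNA at Weeks 12 and 52 will be summarised for all ITT participants with a baseline and a post-baseline value; this is the protocol secondary endpoint.

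Then:

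- Keep T4.04, T4.05, T4.07, T4.08 and F4.02–F4.04 as supportive. Label them as restricted by baseline status, subject to regression to the mean, and to be read with both shift directions in T4.06 and T4.09.
- Confirm that the SAP 8.2 rule for non-detectable laboratory values applies to anti-dsDNA, since negatives will now be included.
- Align SAP 11.1.1 with what is produced. As written it also promises percentage change, and it covers ANA and CRP, which are restricted too but are not in the protocol endpoint.
- If the all-ITT summaries are not added, record the restriction in SAP 2.1 as a change from the protocol.

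The cost is a few tables from data already collected, plus SAP wording. Sample size and trial conduct are unaffected. The all-ITT mean will dilute any effect confined to participants with abnormal values, which is the reason to keep the restricted displays alongside it.
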